### 7.2. Data analysis

Details of the analysis methods will be set out in a specific document entitled "analysis plan", validated by the study's scientific board and made public before the start of the analysis.

The principles guiding the drafting of this analysis plan will be as follows:

General

- The analysis will be performed on an intention-to-treat basis, and will include all centers and all permanent residents, whatever their length of follow-up and reason for premature discharge from the center, with the exception of those who opted out.
- A two-tailed *p-value* of <0.05 is considered statistically significant.

### Main analysis

The main comparison will focus on the incidence of first severe ARI between follow-up periods with an unfiltered UV device and follow-up periods with a filtered UV device. The numerator will be the number of people who experienced at least one severe ARI during a period. The denominator will be the cumulative time spent in the nursing home until the first ARI or exit from the period.

The result will be expressed as an incidence ratio with a 95% confidence interval.

In the first instance, the analysis will be carried out at the individual level. A generalized linear mixed model will be used, with a Poisson distribution or a negative binomial distribution in the case of overdispersion, a logarithmic link function and an *offset* term for the number of patient-years. The model will take into account not only intervention and period fixed effects, but also random effects at cluster, cluster-period, cluster-individual and individual levels. The correlation structure will be of the exchangeable block type.

In the second instance, if the model does not converge, we will perform the analysis at the cluster level (Hayes RJ, Moulton LH. *Cluster Randomised Trials*. CRC Press; 2017. <https://books.google.fr/books?id=iklrDwAAQBAJ> p197).

Sensitivity analyses will be carried out:

- Using the cumulative incidence of severe ARI as the endpoint, with the total number of severe ARI in the numerator and the cumulative time spent in the nursing home until exit from the period in the denominator. The model will be the same as the main model, with the addition of a random individual-period effect.
- By adjusting the model on the following variables: gender, age, GIR index. The last two variables will be measured at the start of each period.

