## Main statistical analysis

The main comparison will focus on the incidence of first severe ARIs between follow-up periods with unfiltered and filtered UV devices. The numerator will be the number of people who experienced at least one acute respiratory infection during a given period. The denominator will be the cumulative follow-up time of participants up to the first acute respiratory infection or exit from the period. The result will be expressed as an incidence ratio with a 95% confidence interval.

In the first instance, the analysis will be carried out at the individual level. A generalized linear mixed model will be used, with a Poisson distribution or a negative binomial distribution in the case of overdispersion, a logarithmic link function and an *offset* term for the number of patient-years. The model will take into account intervention and period fixed effects and random effects at cluster, cluster-period, cluster-individual and individual levels. The correlation structure will be of the exchangeable block type. In the second instance, if the model does not converge, the analysis will be carried out at cluster level.

Sensitivity analyses will be carried out:

- using as endpoint: cumulative incidence of severe acute respiratory infections with the total number of severe acute respiratory infections in the numerator and the cumulative follow-up time to exit from the period in the denominator.

- by adjusting the model on the following variables: age, gender, and GIR index.

Schedule

- Start date: October 1st, 2024
- Follow-up for each period: 7 months + 30 additional days to monitor the evolution of ongoing ARI, hospitalization and AEI at the end of the first 7 months
- End of study: May 31, 2026
- Total study duration: 20 months

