#### 4.3. Primary endpoint

The primary endpoint is the incidence of severe\* symptomatic acute upper and lower respiratory infections†, all grades of severity combined.

\* Severe = leading to oxygen therapy, hospitalization or death

(†) Acute infections considered include sinusitis, otitis media, nasopharyngitis, angina, tracheitis, bronchitis, pulmonary abscess, pneumonia and COPD exacerbations. Documented symptomatic infection with SARS-CoV-2, influenza virus, or respiratory syncytial virus, will be considered by default as a respiratory infection, even in the case of dominant extra-respiratory symptoms.

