#### Morbidity episodes and mortality

Nursing staff will be responsible for monitoring the occurrence of respiratory infections and adverse events of interest, as well as reporting hospitalizations and deaths.

The occurrence of ARIs, AEIs, all-cause hospitalizations, and all-cause deaths will be reported weekly to the trial's clinical research assistants (CRAs) by a designated contact person at each center. The clinical features, as well as any additional examinations prescribed and their results, will be noted in the resident's medical record. CRAs will verify individual reports against predefined diagnostic criteria in the resident's record (and, in case of hospitalisation, in the hospital record) and classify each event as validated (criteria met), rejected (criteria not met), or deferred (uncertain classification pending review). The Clinical Event Review Committee (see section 9.4) will adjudicate deferred events and systematically review all hospitalization and death records. Validated events will be entered into the eCRF by the Clinical Research Assistants (CRAs).

CRAs and the CERC will have secure online access to the electronic care records of participating nursing homes and to hospital records for hospitalized residents. To ensure completeness of event collection, the nursing home software will be queried every three months to generate comprehensive lists of all discharges (death, hospitalization, return home, or transfer to another facility), as well as oxygen and anti-infective prescriptions. These data will be cross-checked against the study database, and any missing or inconsistent events will be investigated and adjudicated by the CERC, in accordance with best practices for independent endpoint review committees.

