#### 6.2.3. Time T2

Time T2 corresponds to the wash-out period (April 1 to September 30, 2025).

During this phase, all UVGI devices will be turned off. No microbiological sampling of air or surfaces will be carried out. ARI and AES will not be monitored. Deaths, hospitalisations and opt-out request will continue to be monitored. New participants will be informed on the study, and their baseline data will be recorded.

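### Section 7.2 limits the primary denominator to time in the home but does not limit the numerator to infections that begin in that time, and the Summary gives a different denominator

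*Protocol*

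**What the plan says.** Section 7.2, Main analysis, fixes both halves of the primary rate. Numerator: "The numerator will be the number of people who experienced at least one severe ARI during a period". Denominator: "The denominator will be the cumulative time spent in the nursing home until the first ARI or exit from the period". The first sensitivity analysis in the same section counts all severe ARIs and again restricts only the denominator to the home.

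The Summary, under Main statistical analysis, describes the same comparison differently: "The denominator will be the cumulative follow-up time of participants up to the first acute respiratory infection or exit from the period".

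Section 4.3 defines severity by consequence: "Severe = leading to oxygen therapy, hospitalization or death". It sets no condition on the place or time of onset. Under Morbidity episodes and mortality (Time T1), research assistants check events "in the resident's record (and, in case of hospitalisation, in the hospital record", and the event review committee looks at every hospitalization and death record.

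On boundaries, section 6.1 has the devices switched on the day each period starts. For the wash-out, the Time T2 section says "ARI and AES will not be monitored". The Time T4 section follows deaths and hospitalizations for a month after period 2 so that they can be tied to an ARI that started before the period ended. Section 6.5.1 collects dates of hospitalization and of leaving and re-entering the home, but its list for ARI episodes contains no onset date.

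**The concern.** An incidence rate needs events and person-time drawn from the same exposure. Section 3.3 places the devices in the communal rooms of the home, so time in the home is a sensible time at risk. Section 7.2 applies that limit below the line and not above it.

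The gap can matter in practice. A resident admitted for a fracture who develops pneumonia and needs oxygen in hospital meets the severity definition, and the trial's own case-finding is built to see the hospital record. As worded, that resident adds one event, while the hospital days in which it arose add nothing to the denominator.

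Devices in the home have little influence on such infections, so they should occur at about the same rate whether the filter is in or out. Their inclusion moves the ratio toward 1. In addition, two statements of the primary analysis that treat absences differently cannot both be followed.

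**Working it through.** **1. The two definitions side by side.** Take a resident who spends a days of the period in the home, is then admitted for a non-respiratory reason, and after b days in hospital develops a first ARI that needs oxygen.

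| Text followed | Events | Person-days |
|---|---|---|
| Section 7.2 | 1 | a |
| Summary | 1 | a + b |
| Onset must fall in home time | 0 | a up to admission |

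Section 7.2 counts an event from b days that it excludes. The Summary's pairing is internally consistent but includes time when the resident was away from the devices. Only the third row matches events to exposed time.

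**2. Effect on the ratio.** Changing the denominator alone does not remove the attenuation. Let T be home time, H hospital time, λ the control rate in the home and μ the rate in hospital, with T, H and μ the same under both conditions (an assumption). Then

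observed ratio = (0.50·λT + μH) / (λT + μH).

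The divisor, T or T + H, cancels. With f = μH / (λT + μH), the share of control-period events that is unaffected,

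observed ratio = 0.50(1 − f) + f = 0.50 + 0.5f.

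**3. Numbers.** The 0.50 is the 50% reduction in section 7.1, assigned here to the preventable events. The documents give no value for f, so the range is assumed.

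| f | Observed ratio | ln(ratio) / ln(0.50) |
|---|---|---|
| 0% | 0.500 | 1.00 |
| 5% | 0.525 | 0.93 |
| 10% | 0.550 | 0.86 |
| 20% | 0.600 | 0.74 |
| 30% | 0.650 | 0.62 |

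**4. The alternative reading of section 7.1.** That section plans the 50% reduction on ARI incidence as a whole. If 0.50 already includes unaffected events, the ratio for the rest would have to be (0.50 − f)/(1 − f): 0.45/0.95 = 0.474 at 5% and 0.40/0.90 = 0.444 at 10%. The observed ratio is then 0.50 as planned, and nothing is lost against the plan. The table in step 3 is therefore conditional.

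**5. Power.** I do not convert this to power. The 12 clusters of section 7.1 are not an input to this point and do not reproduce exactly. With 90 residents per home, ICC 0.1, CAC 0.5, IAC 0.2 and 80% present in both periods, the between-period correlation of cluster means is (90 × 0.1 × 0.5 + 0.9 × 0.2 × 0.8)/9.9 = 0.469. The design effect is 9.9 × (1 − 0.469) = 5.256. Reading 17 and 8.5 per 100 as risks, 12 clusters give 74.0% power, and 14 are needed for 80%. Any power loss quoted from that base would rest on a second unsettled figure as well as on f.

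**The case against.** The best defence is that section 7.2 presents itself as principles for an analysis plan to be written later. Events are also validated against predefined diagnostic criteria that the protocol does not reproduce. Onset and attribution rules often sit in such documents. That would answer a complaint about missing detail. It does not answer a numerator and denominator that section 7.2 states outright, or a Summary that contradicts it: a plan that follows section 7.2 inherits the mismatch.

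A second defence is that counting every severe ARI in residents is a pragmatic intention-to-treat effect. That is a legitimate choice, but it concerns who is analysed and under which allocation. If all severe ARIs are meant, hospital time belongs in the denominator and section 7.2 still needs changing.

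A third objection stands in part. Place of onset is not place of acquisition. An onset rule drops infections caught in the home that surface just after admission, and keeps infections incubated in hospital that surface after return. This is why excluded events should be added back in a sensitivity analysis.

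A reader might infer that the plan counts infections already present on arrival or begun before switch-on. The documents do not say so. The measure is incidence within a period that starts on the switch-on day, and the one-day presence rule in section 5.1 is about which residents are eligible, not which infections are incident. Nor is there a stated rule that treats the two ends of the period differently. The protocol uses onset at the end of period 2 and is silent at the start.

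**Conclusion.** The concern holds in limited form. Section 7.2 restricts the denominator to time in the home without restricting the numerator to severe ARIs that begin there, and the Summary gives a different denominator. Followed as written, hospital-onset severe ARIs can count without person-time and would bias the ratio toward 1. The direction rests on these events being about equally frequent under both conditions.

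The size is unknown. The figures of 0.525 at 5% and 0.55 at 10% are illustrations under an assumed f, with 0.50 applied to the preventable events; they are not an estimate of loss against the planned effect. It would also be too strong to call the rate uninterpretable: on the same assumption the error is conservative attenuation, possibly small. This is a worthwhile and inexpensive correction, not a threat to the trial's validity.

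**What to change.** Before unblinding:

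- Use one denominator, time in the home, in section 7.2 and in the Summary, for the main analysis and for the sensitivity analysis on total events.
- Count a severe ARI in the primary numerator only if its onset falls in that time at risk within the period. This extends to the start of each period the onset-based attribution that the Time T4 section uses at the end of period 2.
- List hospital-onset ARIs separately and include them in a sensitivity analysis. State whether such an event ends a resident's time at risk or whether home time resumes on return.
- Optionally, add a sensitivity analysis that starts time at risk and event counting after a short lag from switch-on, admission to the home or return from hospital.

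Absence and re-entry dates are already collected. The cost is slightly fewer counted events, plus the work of dating onset from the medical record, blind to filter state, because section 6.5.1 lists no onset date. Version 3 of the protocol is dated after period 1 ended, so some events already validated may need a second look. ARIs were not monitored in the wash-out, so any onset shortly before 1 October 2025 would also have to come from the records.

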#### 4.4. Secondary endpoints

The secondary endpoints are:

1. Incidence of symptomatic ARIs of any severity
2. Incidence of non-infectious adverse events of interest††, overall and by severity grade (CTCAE classification)
3. Incidence of all-cause hospitalization or death (separately and combined)
4. Total antibiotic consumption, overall and by class
5. Viral load in air samples collected in communal living spaces
6. Viral, bacterial and fungal load on surface (fomite) samples collected in communal living areas
7. Incremental Cost-Effectiveness Ratio (ICER) of UVGI implementation.

(††) Keratitis and erythematous skin eruptions occurring in light-exposed areas.

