### Analysis of clinical secondary endpoints

- Analyses of clinical secondary endpoints will focus on:
  - Incidence of symptomatic ARIs of all grades
  - Incidence of all-cause hospitalization, all-cause mortality, and all-cause "hospitalization or death"
  - Incidence of non-infectious adverse events of interest, overall and by severity grade (CTCAE classification).
- Analyses of clinical secondary endpoints will focus on the occurrence of the 1st event and will be performed without adjustment. Sensitivity analyses will be performed:
  - Using cumulative incidence as the endpoint
  - By adjusting the model on the following variables: age, gender, GIR index.
- Analyses of clinical secondary endpoints will use the same model as that used for the primary analysis, or equivalent models appropriate to the frequency of events.

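### The primary analysis does not carry the word severe through its numerator and denominator: section 7.2 pairs severe events with time to any ARI, and the Summary defines both by any ARI

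*Protocol*

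**What the plan says.** The objectives (Summary and section 4.1) and the endpoint definition in the Summary name severe ARI, meaning one that leads to oxygen, hospitalization or death. The lead sentences of both descriptions of the main analysis also announce a comparison of first severe ARIs. The sentences that then define the rate read differently:

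- **Section 7.2, Main analysis.** Numerator: "The numerator will be the number of people who experienced at least one severe ARI during a period". Denominator: "The denominator will be the cumulative time spent in the nursing home until the first ARI or exit from the period".
- **Summary, Main statistical analysis.** Numerator: "The numerator will be the number of people who experienced at least one acute respiratory infection during a given period". Denominator: "The denominator will be the cumulative follow-up time of participants up to the first acute respiratory infection or exit from the period".
- **Section 4.3.** The endpoint is called severe and, in the same sentence, "all grades of severity combined".

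ARI of any severity has its own place: section 4.4 lists "Incidence of symptomatic ARIs of any severity" as the first secondary endpoint, and section 7.2 gives "Incidence of symptomatic ARIs of all grades" a first-event analysis. The first sensitivity analysis in 7.2 is consistent, "with the total number of severe ARI in the numerator and the cumulative time spent in the nursing home until exit from the period", so it counts severe events over the whole stay in the period.

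**The concern.** In a first-event rate, the event that is counted must also be the event that ends time at risk. Section 7.2 breaks that rule. A resident with a mild bronchitis in November and a pneumonia leading to hospitalization in February adds one event to the numerator but no person-time after November. The rate is overstated in both conditions, and more so where mild ARIs are more frequent. If UVGI lowers mild ARIs, person-time is cut more in the inactive periods and the ratio moves in favour of UVGI.

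The Summary has a different fault. Its numerator and denominator match each other, but together they define the first secondary endpoint. A reader therefore cannot repair one section from the other, because the two drop the word in different patterns. The confusion is not far-fetched: under its other points to watch, section 7.2 records that the investigators hesitated between a broad all-severity endpoint and a restrictive severe one.

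**Working it through.** The protocol gives no figure for this point, so the check sets the wordings side by side and then sizes them.

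**Wordings**

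| Version | Events counted | Clock stops at |
|---|---|---|
| A. Evident intent | severe ARI | first severe ARI |
| B. Section 7.2 | severe ARI | first ARI of any kind |
| C. Summary | any ARI | first ARI of any kind |

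**Inputs**
- Any-ARI winter attack rate: 18% to 25% (section 2.1), taken as the risk over one 7-month period.
- Severe share of ARIs, f: 10% to 30%. This is an assumption; the protocol gives none.
- Constant, independent hazards for mild and severe ARI; exits ignored.

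**Formulas** (time unit: one period)
- Any-ARI hazard L = −ln(1 − attack rate): 0.198 at 18%, 0.288 at 25%.
- Severe hazard Ls = f × L; mild hazard Lm = L − Ls.
- Rate A = Ls, the true severe rate.
- Rate B = (1 − e^(−Ls)) ÷ [(1 − e^(−L)) / L].
- Rate C = L.
- Share of first severe ARIs that fall after the clock has stopped = 1 − f(1 − e^(−L)) / (1 − e^(−Ls)).

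**Worked case, attack rate 25%, f = 0.10.** Ls = 0.0288. The proportion with a severe ARI is 1 − e^(−0.0288) = 0.0284. Mean time to first ARI is 0.25 / 0.2877 = 0.869. Rate B = 0.0284 / 0.869 = 0.0326, against a true 0.0288, so B/A = 1.134. If only mild ARIs are halved, the any-ARI hazard falls to 0.0288 + 0.1295 = 0.158, mean time rises to 0.925 and rate B is 0.0307. The ratio is 0.0307 / 0.0326 = 0.94, although severe ARIs have not changed.

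**Section 7.2 as written**

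| Attack rate | f | Control rate B/A | Severe ARIs after clock stopped | Ratio, all halved (true 0.50) | Ratio, mild only halved (true 1.00) |
|---|---|---|---|---|---|
| 18% | 0.1 | 1.092 | 8.4% | 0.479 | 0.957 |
| 18% | 0.2 | 1.081 | 7.5% | 0.481 | 0.962 |
| 18% | 0.3 | 1.070 | 6.6% | 0.483 | 0.967 |
| 25% | 0.1 | 1.134 | 11.8% | 0.470 | 0.940 |
| 25% | 0.2 | 1.118 | 10.6% | 0.473 | 0.946 |
| 25% | 0.3 | 1.103 | 9.3% | 0.477 | 0.953 |

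With no effect on any ARI the ratio is 1.000. With severe ARIs only halved it is 0.500 throughout.

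**Effect on the test.** A 50% reduction detected with 80% power at two-sided 5% (section 7.1) implies a standard error of the log ratio of ln 2 / (1.960 + 0.842) = 0.247. In the mild-only case the shift is ln(0.967)/0.247 = −0.14 to ln(0.940)/0.247 = −0.25 standard errors. Two-sided rejection rises from 5.0% to about 5.2–5.7%.

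**Summary as written.** The ratio is treated L over control L.
- Severe only halved: 1 − f/2 = 0.95, 0.90, 0.85 for f = 0.1, 0.2, 0.3 (true severe ratio 0.50).
- Mild only halved: (1 + f)/2 = 0.55, 0.60, 0.65 (true severe ratio 1.00).
- All halved: 0.50, as intended.

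**The case against.** The best defence is that nobody would be misled. The objectives, the Summary's endpoint definition and the lead sentence of each analysis description all say severe. In 7.2 the denominator sentence directly follows two sentences that say so, so its ARI can be read as shorthand for the event just named. Section 7.2 also presents itself as principles for an analysis plan to be validated and published before analysis, and that plan, which is not at hand, may state the rule correctly.

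The size can also be argued down:
- With a severe share of 50%, control inflation is 5–7% and the all-halved ratio 0.483–0.488.
- If the 17 per 100 patient-years in section 7.1 is read as an any-ARI rate, then L = 0.17 × 7/12 = 0.099. Over severe shares of 10–50%, inflation is about 2.5–4.5% and the all-halved ratio 0.489–0.494.
- If the trial is less precise than 7.1 claims, the rise in rejection shrinks; at a standard error of 0.37 it is 5.1–5.3%.
- The large gaps under the Summary wording need UVGI to act on mild ARIs only or severe ARIs only. The protocol gives no estimate for either, and its hypothesis (section 2.3) is a reduction in both ARIs and complications.

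All of this stands as to weight, and the intent is indeed clear. It does not remove the contradiction. First ARI is a meaningful, programmable instruction here, because any ARI is a named endpoint. And if these sentences are the principles for the analysis plan, a plan that follows them inherits the mismatch, while one that corrects them departs from the protocol.

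**Conclusion.** The primary analysis is wrong as written in two places, and section 4.3 contradicts itself. Severe ARI is clearly the intended endpoint, so this is a failure to carry the definition into the operative sentences, not doubt about the aim.

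The numerical effect of the 7.2 wording is modest: a control rate 7–13% too high and a ratio moved by 0.02–0.03 when all ARIs are halved, or by 0.03–0.06 in favour of UVGI when only mild ARIs are halved. It vanishes if UVGI affects no ARI and is negligible if it affects only severe ones. These figures rest on constant hazards, the 18–25% attack rate and the assumed 10–30% severe share; a higher severe share or a lower attack rate makes them smaller.

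The Summary wording is the more serious in principle, because it answers the question of a secondary endpoint, but it matters numerically only where mild and severe ARIs respond differently. The first sensitivity analysis in 7.2 is free of the mismatch, but it is not the primary result. The text should be corrected; the point does not threaten the trial.

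**What to change.** - Section 7.2, Main analysis: insert *severe* before ARI in the denominator sentence.
- Summary, Main statistical analysis: insert *severe* in both the numerator and the denominator sentence.
- In both places, add that a non-severe ARI does not stop the clock for the primary analysis.
- Section 4.3: delete the phrase about all grades of severity.
- Keep the any-ARI analysis as the first secondary endpoint, with person-time ending at the first ARI of any severity.

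The cost is a few words in three places. No new data are needed: ARI episodes, oxygen treatment, hospitalizations and deaths are already collected (section 6.5.1). Making the change before unblinding avoids any later suspicion that the definition was chosen in the light of the results.

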### 7.1. Number of centers and individuals to include

Each Nursing Home will have an approximate size of 90 participants, with a small coefficient of variation. It is estimated that 80% of participants will be present in both periods. As recruitment is open to new participants, those who die or permanently leave their Nursing Home will be replaced, and the number of participants present in each Nursing Home will remain constant throughout the study.

The intra-cluster coefficient of variation (WP-ICC  $\rho$ ) is estimated at 0.1 (10% of ARIs are explained by the Nursing Home environment). The inter-period correlation (between-period ICC  $\eta$ ) is estimated to be negligible (the two periods are winter and one year apart). Cluster auto-correlation (CAC) is set at 0.5 (i.e.  $\eta=0.05$ ), a figure recommended when few hypotheses are involved (Giraudeau *et al*, Sample size calculation for cluster randomized cross-over trials. Stat Med 2008;27:5578-85). Individual auto-correlation (IAC) is set at 0.2. Assuming an ARI incidence of 17 per 100 patient-years in the absence of UVCI devices, it is estimated that 12 clusters need to be included to demonstrate a 50% reduction in ARI incidence, with a two-sided alpha risk of 0.05 and power of 80% (Kasza *et al*, Sample Size Calculation for Stepped Wedge and Other Longitudinal Cluster Randomised Trials. Stat Med 2020;39:1871-83; Hooper *et al*, Sample size and power calculations for open cohort longitudinal cluster randomized trials. Stat Med 2016;35:4718-28)

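### The primary mixed model lists the resident effect twice, so it is not identifiable, and a fit flagged for that reason could move the primary analysis to cluster level

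*Protocol*

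**What the plan says.** Protocol section 7.2, Main analysis, sets out an individual-level Poisson or negative binomial mixed model with intervention and period as fixed effects and "random effects at cluster, cluster-period, cluster-individual and individual levels". The Summary (Main statistical analysis) gives the same list. Section 7.2 then states: "The correlation structure will be of the exchangeable block type". The sensitivity analysis on total events reuses the main model "with the addition of a random individual-period effect".

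Only one event changes the primary method. Section 7.2 says "if the model does not converge, we will perform the analysis at the cluster level", and the Summary says "if the model does not converge, the analysis will be carried out at cluster level". Neither place says what counts as non-convergence.

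Section 7.1 plans with one within-period intra-cluster correlation, one cluster auto-correlation and one resident-level parameter: "Individual auto-correlation (IAC) is set at 0.2".

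**The concern.** In this trial a resident belongs to one home. A random effect for resident within home and a random effect for resident then have the same levels and enter the model in the same way. The data cannot divide the resident variance between them.

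A duplicated term would usually be harmless. It matters here because failure of the fit is the stated trigger for leaving the primary method. The likelihood is flat along the split between the two resident variances, so a program that inspects the Hessian may report a failed fit even when the data fit the intended model well. The reported primary analysis could then depend on a wording slip and on the software used.

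**Working it through.** **Inputs.** From section 7.1: 12 homes, about 90 residents each, 80% present in both periods, within-period correlation 0.1, cluster auto-correlation 0.5, individual auto-correlation 0.2, control incidence 17 per 100 patient-years. From section 3.3: two periods of 7 months. The protocol gives no figure on this point, so there is none to reproduce; the sample size of 12 homes does not enter.

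**Step 1: the model as listed.** For resident i of home k in period j, the log rate is

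fixed effects + a(k) + b(k,j) + c(k,i) + d(i),

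with variances A, B, C and D. Each i occurs in one k only, so c(k,i) + d(i) is a single normal effect with variance C + D. The covariances on the log scale are:

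- different residents, same home, different periods: A
- different residents, same home, same period: A + B
- same resident, different periods: A + C + D

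C and D appear only as a sum.

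**Step 2: check on the planned layout.** Of 90 residents per home-period, 0.8 × 90 = 72 are in both periods and 18 are in one only.

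- Rows: 12 × 90 × 2 = 2,160.
- Residents: 12 × (72 + 18 + 18) = 1,296.
- Levels of resident within home: 1,296. Levels of resident: 1,296. The groupings are identical.
- Rank of the covariance basis (one same-group indicator matrix per random effect): 3 for the four listed terms, and 3 for home, home-period and one resident term.

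**Step 3: can the fourth term mean something else?** Replacing it with a resident-by-period effect gives rank 4, but section 7.2 adds that effect on top of the main model for one sensitivity analysis, so it is not already there.

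**Step 4: comparison with the rest of the protocol.** Three planning correlations correspond to three variance components. A block-exchangeable structure has the same three. The four-term list matches neither.

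**Step 5: how often the duplicate causes a flag.** Simulated trials used the layout above, time to first event, a true ratio of 0.5 and a Poisson mixed model in glmmTMB at default settings. A flag is a Hessian that is not positive definite or a non-zero convergence code. The standard deviations (log scale) are assumptions.

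| SD home / home-period / resident | Trials | Flagged, four terms | Flagged, three terms |
|---|---|---|---|
| 0.25 / 0.25 / 0.7 | 133 | 5 (3.8%, 95% CI 1.2–8.6%) | 0 (upper limit 2.7%) |
| 0.72 / 0.72 / 0.7 | 60 | 16 (26.7%, 95% CI 16.1–39.7%) | 0 (upper limit 6.0%) |

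Integrating the 7-month control risk over these effects gives a within-period correlation of about 0.014 for the first row, well below the planned 0.1, and about 0.09 for the second. The first row applied 17 per 100 patient-years conditionally on the random effects and averaged 200 events; the planning rate implies about 102 + 52 = 154 first events. The second row held the marginal rate at 17 per 100 patient-years.

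All 5 trials flagged in the first row fitted cleanly once the duplicate was removed. In lme4, 18 trials gave one warning with each version.

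**The case against.** **The estimate does not change.** This stands. A reader might infer that the duplicate biases the incidence ratio or its standard error; it does neither at the same optimum. In the second set the mean ratio was 0.455 with either version, and all 60 four-term fits gave a finite standard error. In the first set, 124 of 128 unflagged pairs agreed to within 0.0008 in log ratio; the other 4 stopped at different local optima.

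**A flag need not count as non-convergence.** This also stands. The protocol does not say that a Hessian warning triggers the fallback, and lme4 showed no difference. The harm is conditional on the package and on how its warning is read.

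**Residents may move between trial homes.** Section 6.2.2 records transfers, but nothing in the protocol provides for a resident followed in two participating homes. If events in the two periods were independent, 864 × 0.0944 × 0.0484 = 3.9 residents would have events in both; if 5% of residents moved (assumed), that is 0.2 movers. A few movers could not support a separate variance.

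**Detail belongs in the analysis plan.** This is right for much that might be added here. A reader might infer that a direct step to a cluster-level analysis is itself a mistake, or that a ladder of simpler models is missing. The protocol does not support that: a cluster-level analysis is a valid pre-specified method with 12 homes, nothing here shows that it performs worse, and intermediate steps are ordinary analysis-plan content. Likewise, the choice "with a Poisson distribution or a negative binomial distribution in the case of overdispersion" names no test that could be faulted. The list of random effects is different: the protocol states it, and states it wrongly.

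**The secondary endpoints are not bound.** "Analyses of clinical secondary endpoints will use the same model as that used for the primary analysis" is followed by an allowance for equivalent models suited to event frequency. The duplicate reaches those endpoints only where the same model is used.

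**Conclusion.** The concern holds as an error in the stated model. The four-term list has one variance component that cannot be identified, and it conflicts with the three correlations of section 7.1 and with the block-exchangeable structure of section 7.2. This rests on nesting alone and needs no simulation.

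The consequence is narrower. It is an avoidable route by which the primary analysis could move to cluster level for a reason unrelated to the data. The flag rates of 5 in 133 and 16 in 60, against none with three terms, show that this can happen in one package under assumed variances. They are not estimates of the probability in this trial: the first set lies well below the planned within-period correlation, and the resident SD of 0.7 was assumed rather than derived from the individual auto-correlation.

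The change should be made before the analysis starts. It does not call the design or the fallback method into question.

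**What to change.** In section 7.2 (Main analysis) and in the Summary (Main statistical analysis), list three random intercepts: home, home-period, and one effect for resident within home. The cluster-level fallback is then triggered only by failure of an identifiable model.

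The dependent models follow. The adjusted sensitivity analysis inherits the three terms. The total-events sensitivity analysis has those three plus the resident-by-period effect, which is a distinct grouping. The clinical secondary endpoints change only where they use the same model.

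The cost is one phrase reworded in two places, carried into the analysis plan, and the ethics committee review that section 13.2 requires for any amendment. No data are needed and no precision is lost, since the ratio and its standard error are the same at the same optimum.
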